12.1.7 Response Review

Response will be measured by RECIST criteria.

13. DATA REPORTING / REGULATORY REQUIREMENTS

Adverse event lists, guidelines, and instructions for AE reporting can be found in Section 7.0 (Adverse Events: List and Reporting Requirements).

13.1 Data Reporting

13.1.1 Method

Cumulative protocol- and patient-specific data will be submitted electronically into ONCORE monthly.

13.1.2 Responsibility for Data Submission

Study staff are responsible for submitting data and/or data forms in ONCORE per Winship SOP 4.2 Data Completion Metrics. Data completion will be reviewed monthly. In situations where there are significant delays of data completion, the PI may temporarily suspend enrollment. Data entry is to be completed within the designated timeframe, not to exceed 30 days of the subject visit.

Queries will be resolved by the research staff within the time frame specified by the protocol, not to exceed 2 weeks.

The Data and Safety Monitoring Committee (DSMC) of the Winship Cancer Institute will provide oversight for the conduct of this study. The DSMC functions independently within Winship Cancer Institute to conduct internal monitoring functions to ensure that research being conducted by Winship Cancer Institute Investigators produces high-quality scientific data in a manner consistent with good clinical practice (GCP) and appropriate regulations that govern clinical research. Depending on the risk level of the protocol, the DSMC review may occur every 6 months or annually. For studies deemed High Risk, initial study monitoring will occur within 6 months from the date of the first subject accrued, with 2 of the first 5 subjects being reviewed. For studies deemed Moderate Risk, initial study monitoring will occur within 1 year from the date of the first subject accrued, with 2 of the first 5 subjects being reviewed. Subsequent monitoring will occur in routine intervals per the Winship Data and Safety Monitoring Plan (DSMP).

The DSMC will review pertinent aspects of the study to assess subject safety, compliance with the protocol, data collection, and risk-benefit ratio. Specifically, the Winship Cancer Institute Internal Monitors assigned to the DSMC may verify informed consent, eligibility, data entry, accuracy and availability of source documents, AEs/SAEs, and essential regulatory documents. Following the monitoring review, monitors will provide a preliminary report of monitoring findings to the PI and other pertinent individuals involved in the conduct of the study. The PI is required to address and respond to all the deficiencies noted in the preliminary report. Prior to the completion of the final summary report, monitors will discuss the preliminary report responses with the PI and other team members (when appropriate). A final monitoring summary report will then be prepared by the monitor. Final DSMC review will include the final monitoring summary report with corresponding PI response, submitted CAPA (when applicable), PI Summary statement, and available aggregate toxicity and safety data.

The DSMC will render a recommendation and rating based on the overall trial conduct. The PI is responsible for ensuring that instances of egregious data insufficiencies are reported to the IRB. Continuing Review submissions will include the DSMC recommendation letter. Should any revisions be made to the protocol-specific monitoring plan after initial DSMC approval, the PI will be responsible for notifying the DSMC of such changes. The Committee reserves the right to conduct additional audits if necessary.

14. STATISTICAL CONSIDERATIONS

14.1 Study Design/Endpoints

Endpoints:

Primary:

• Primary endpoint is the rate of CTC (v5.0) grade 3 or greater immune-related adverse events at 6 months of follow up.

Secondary:

- Rate of CTC (v5.0) toxicity related to Rituxan.
- Objective tumor response as assessed by RECIST v1.1 and irRECIST at 12 weeks and every 12 weeks thereafter.
- Rates of overall and progression-free survival at 1 year following initiation of therapy.

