This is a prospective randomized trial to test the efficacy of preemptive Rituxan in melanoma patients in reducing Immune-related adverse events (IRAEs) following combination checkpoint blockade (CCB). All eligible patients will undergo baseline evaluation to assess the status of disease as well as a baseline tumor biopsy. Combination checkpoint blockade will be administered as per current FDA approved standard of care, consisting of nivolumab at a dose of 1 mg/kg and ipilimumab at a dose of 3 mg/kg every 3 weeks for 4 doses, followed by nivolumab maintenance at a dose of 480 mg every 4 weeks x 1 year. Patients will be randomly assigned to no additional therapy (ARM A control) or 4 weekly doses of Rituxan for B cell depletion (ARM B). Rituxan will be administered as 375 mg/m2 IV for the first dose followed by weekly subcutaneous dosing at 1400 mg dose of Rituxan Hycela for weeks 2-4, as per recommended dosing for the FDA approval in the setting of lymphoma. All patients will be clinically monitored for the development of IRAEs utilizing NCI Common Toxicity Criteria v5.0. Any patient who received at least one dose of study drug will be included in safety analysis, and safety assessment will continue through treatment phase and up to 100 days after the last dose of study drug. Tumor response will be assessed according to the Response Evaluation Criteria in Solid Tumors (RECIST v1.1) and irRECIST at 12 weeks and every 12 weeks thereafter. All patients will also undergo pre treatment and post treatment biopsies if possible.

TABLE OF CONTENTS

SCH	EMA	3								
1.	OBJECTIVES	6								

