1.2 Secondary Objectives

- To evaluate the safety and tolerability (in terms of Rituxan-related adverse events) in patients with melanoma receiving CCB.
- To compare objective response rate in patients receiving CCB therapy + Rituxan versus CCB therapy alone.
- To compare 1 year overall and progression-free survival in patients receiving CCB therapy + Rituxan versus CCB therapy alone.
- To compare changes in CD21^{lo} B cells in patients receiving CCB therapy + Rituxan versus CCB therapy alone.
- To compare changes in T cells in patients receiving CCB therapy + Rituxan versus CCB therapy alone.

Exploratory Objectives

• To compare treatment induced changes in tumor tissue in patients receiving CCB therapy + Rituxan versus CCB therapy alone.

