
Local Cutaneous Reactions

Local cutaneous reactions, including injection site reactions, have been reported in patients receiving RITUXAN HYCELA. Symptoms included pain, swelling, induration, hemorrhage, erythema, pruritus, and rash. Some local cutaneous reactions occurred more than 24 hours after RITUXAN HYCELA administration. The incidence of local cutaneous reactions following administration of RITUXAN HYCELA was 16%. Reactions were mild or moderate and resolved without any specific treatment. Local cutaneous reactions of any Grade were most common during the first RITUXAN HYCELA cycle (Cycle 2; 5%) with the incidence decreasing with subsequent injections.

Tumor Lysis Syndrome (TLS)

TLS can occur within 12–24 hours after administration of a rituximab-containing product, including RITUXAN HYCELA. A high number of circulating malignant cells (≥ 25,000/mm3) or high tumor burden confers a greater risk of TLS. Administer aggressive intravenous hydration and anti-hyperuricemic therapy in patients at high risk for TLS. Correct electrolyte abnormalities, monitor renal function and fluid balance, and administer supportive care, including dialysis as indicated.

Infections

Serious, including fatal, bacterial, fungal, and new or reactivated viral infections can occur during and following the completion of therapy with rituximab-containing products, including RITUXAN HYCELA. The incidence of infections with RITUXAN HYCELA vs rituximab was 56% and 49% respectively in patients with CLL, and 46% and 41% respectively in patients with FL/DLBCL in combination with chemotherapy. Infections have been reported in some patients with prolonged hypogammaglobulinemia (defined as hypogammaglobulinemia > 11 months after rituximab exposure). New or reactivated viral infections included cytomegalovirus, herpes simplex virus, parvovirus B19, varicella zoster virus, West Nile virus, and hepatitis B and C. Discontinue RITUXAN HYCELA for serious infections and institute appropriate anti-infective therapy.

Cardiovascular Adverse Reactions

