7.2 Adverse Event Characteristics

SAFETY REPORTING OF ADVERSE EVENTS

ASSESSMENT OF SAFETY

Specification of Safety Variables

Safety assessments will consist of monitoring and reporting adverse events (AEs) and serious adverse events (SAEs) per protocol. This includes all events of death, and any study specific issue of concern.

Adverse Events

An AE is any unfavorable and unintended sign (including an abnormal laboratory finding), symptom, or disease temporally associated with the use of an investigational medicinal product (IMP) or other protocol-imposed intervention, regardless of attribution.

This includes the following:

- AEs not previously observed in the subject that emerges during the protocol-specified AE reporting period, including signs or symptoms associated with melanoma those were not present prior to the AE reporting period.
- Complications that occur as a result of protocol-mandated interventions (e.g., invasive procedures such as cardiac catheterizations)
- If applicable, AEs that occur prior to assignment of study treatment associated with medication washout, no treatment run-in, or other protocol-mandated intervention.
- Preexisting medical conditions (other than the condition being studied) judged by the
- Investigator to have worsened in severity or frequency or changed in character during the protocol-specified AE reporting period.

Serious Adverse Events

An AE should be classified as an SAE if the following criteria are met:

- It results in death (i.e., the AE actually causes or leads to death).
- It is life threatening (i.e., the AE, in the view of the investigator, places the subject at immediate risk of death. It does not include an AE that, had it occurred in a more severe form, might have caused death.).
- It requires or prolongs inpatient hospitalization.
- It results in persistent or significant disability/incapacity (i.e., the AE results in substantial disruption of the subject's ability to conduct normal life functions).
- It results in a congenital anomaly/birth defect in a neonate/infant born to a mother exposed to the IMP.
- It is considered a significant medical event by the investigator based on medical judgment (e.g., may jeopardize the subject or may require medical/surgical intervention to prevent one of the outcomes listed above).

METHODS AND TIMING FOR ASSESSING AND RECORDING SAFETY VARIABLES

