14.2 Sample Size/Accrual Rate

This is an open-label, 2-arm phase II clinical trial to study the differential effect in the risk of IRAEs between treatment and control groups. A sample size of 22 patients per arm (44 total) will provide us approximately 80% power to detect a 40% difference in the rates of developing ≥grade 3 IRAE within 6 months follow up between the control and the treatment arm (estimated to be 60% in the control arm, Callahan et al; J Clin Oncol. 2017 Dec 1;35(34):3815-3822). The sample size calculation is based on Fisher's exact test at a one sided significance level of 0.05 under the following assumptions: 1). Patients will be randomized in 1:1 ratio of the treatment to control arm. 2). Approximately 60% patients in the placebo arm will develop > grade 3 IRAE

within 6 months based on our pilot study. 3). The treatment will reduce the rate of ≥ grade 3 IRAE to 20% in the treatment arm. In a recent study, the rate of objective response following combination checkpoint blockade was 42% (Callahan et al; J Clin Oncol. 2017 Dec 1;35(34):3815-3822). In order to monitor potentially adverse impact of Rituxan on checkpoint blockade, we will utilize early stopping rules based on an adaptive design wherein trial will be stopped if we have strong evidence of rates of objective response of <30%. The trial will be stopped early in the unlikely event that less than 2 patients among the first 12 patients treated by Rituxan respond to therapy. If the rate of objective response is > 30%, the probability that at least two out of first twelve patients will achieve an objective response of at least a PR for the first 12 patients is approximately 92%. Hazard ratios and corresponding two-sided 95% confidence intervals will be estimated using Cox-proportional hazards model, with the treatment group as a single covariate. Progression-free and overall survival curves, median with 95% confidence intervals, and progression-free survival rates at 6 months will be estimated with the use of Kaplan-Meier method. Biostatistics support for the study will be provided by biostatistics core resource of Winship Cancer Center.

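### The only Rituxan safety endpoint depends on attribution and has no Arm A counterpart, and no between-arm comparison of all-cause severe events, infections or SAEs is specified

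*Combined protocol and SAP*

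**What the plan says.** Section 14.1 has two endpoints on toxicity.

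- **Primary:** "Primary endpoint is the rate of CTC (v5.0) grade 3 or greater immune-related adverse events at 6 months of follow up". Section 14.2 powers this as a comparison between arms.
- **Secondary:** "Rate of CTC (v5.0) toxicity related to Rituxan". No grade threshold, time window or comparator is given.

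The matching objective in section 1.2 is "To evaluate the safety and tolerability (in terms of Rituxan-related adverse events) in patients with melanoma receiving CCB". The other four secondary objectives are worded as comparisons between arms. Section 14.2 states "This is an open-label, 2-arm phase II clinical trial", and under the Schema and section 5.1 Arm A receives ipilimumab and nivolumab without Rituxan.

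Data collection is broader than the endpoint. Section 7.2 ties an adverse event to an investigational product or "other protocol-imposed intervention, regardless of attribution". Section 7.4 sends all adverse events to the study database, section 7.3.2 requires serious events to be reported whether related or not, and section 12.1.1 makes every patient evaluable for toxicity from the first ipilimumab/nivolumab dose.

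Section 7.1 lists the known risks of rituximab. On infection it says "Serious, including fatal, bacterial, fungal, and new or reactivated viral infections can occur during and following the completion of therapy".

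**The concern.** The trial asks whether adding Rituxan makes combination blockade less toxic. That needs two things: fewer immune-related events, and no offsetting rise in other severe events. Only the first has a pre-specified randomised comparison. The second rests on a one-arm rate that depends on how investigators who know the allocation assign cause. Every patient also has advanced melanoma and receives ipilimumab/nivolumab, so another explanation for an infection or a cytopenia is often at hand.

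Nothing else in the plan fills the gap. The early stopping rules in section 14.2 concern tumour response only. The monitoring committee in section 13.1.2 sees aggregate toxicity data, with no comparison by arm specified. The trial could therefore report a lower IRAE rate without a planned check on severe toxicity overall.

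**Working it through.** **1. The plan's own figure.** The inputs from section 14.2 are 22 per arm, 60% versus 20%, and a one-sided Fisher's exact test at 0.05. Power is the sum of Bin(a; 22, 0.60) × Bin(b; 22, 0.20) over all (a, b) with p ≤ 0.05. This gives 79.1%, against the stated approximately 80%. The figure reproduces and is not in dispute.

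**2. Where a severe event is counted.**

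| Event | Endpoint that counts it | Compared between arms? |
|---|---|---|
| Judged immune-related | Primary | Yes |
| Judged related to Rituxan | Secondary | No, Arm B only |
| Fatal, any cause | 1-year OS and PFS | Yes, without cause |
| Non-fatal, judged neither | None | No |

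The last row is the gap.

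**3. How far the Rituxan-related rate depends on attribution.** These rates are assumptions, because the documents give none. Let non-immune severe events occur in 10% of Arm A and 30% of Arm B, an excess of 20 points, and let a fraction f of that excess be attributed to Rituxan. The expected related rate is 0.20f, and P(no related event in 22) = (1 − 0.20f)^22.

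- f = 0.25: rate 5%, probability 0.95^22 = 32%
- f = 0.50: rate 10%, probability 0.90^22 = 10%
- f = 0.75: rate 15%, probability 0.85^22 = 3%
- f = 1: rate 20%, probability 0.80^22 = 0.7%

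One true excess can therefore give anything from an empty listing to a clear signal, depending on f.

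**4. Why an any-cause grade 3 or greater rate is not enough alone.** Assume a background non-immune rate c in both arms, independent of IRAEs, and no harm from Rituxan. The any-cause difference is [1 − 0.40(1 − c)] − [1 − 0.80(1 − c)] = 0.40(1 − c). At c = 20% this is 32 points. Now set c = 0 and let Rituxan add events in 10% of Arm B. The difference is 60% − [1 − 0.80 × 0.90] = 60% − 28% = 32 points again. Dilution and harm look the same, so infections and non-immune events need their own lines.

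**5. Precision with 22 per arm.** The approximate 95% half-width is 1.96 × √[(p₁(1 − p₁) + p₂(1 − p₂))/22].

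- 5% vs 15%: 17.5 points
- 10% vs 30%: 22.9 points
- 20% vs 40%: 26.4 points
- 60% vs 28%: 27.8 points

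One-sided Fisher power for 10% vs 30% is 38%.

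**6. Whether the data will exist for 6 months.** The Schema defines the safety set as patients with at least one dose of study drug and runs assessment to 100 days after the last dose. Section 7.2 stops at 30 days after the last study treatment or at discontinuation, whichever is earlier. After that it asks only for attributed SAEs and, under post-study events, all deaths. Section 5.2 limits protocol-specific therapy to rituximab, while section 12.1.1 counts every patient from the first ipilimumab/nivolumab dose.

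The study calendar places the last Rituxan dose in week 5. If study treatment means Rituxan, 30 days (4.3 weeks) ends near week 9 and 100 days (14.3 weeks) near week 19. Both fall before 6 months (about week 26), and neither has an anchor in Arm A. If it includes nivolumab, patients whose last dose falls before about week 22 (26 − 4.3) still leave the 30-day window early. Section 2.3 reports discontinuation in up to one third of patients on combination blockade.

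**The case against.** The case on the other side is substantial.

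- A reader might infer that Rituxan's safety is measured only through attributed events. The documents do not support that: sections 7.2, 7.3.2, 7.4 and 12.1.1 record events without regard to attribution. The gap lies in the specified endpoint and analysis.
- A reader might also infer that liver, lung or bowel toxicity would escape both endpoints. Severe organ toxicity put down to checkpoint blockade would ordinarily be called immune-related and enter the compared primary endpoint. Section 3.1 also excludes patients with current or past hepatitis B or C. Infections and cytopenias are the stronger examples.
- Under-attribution is possible but not shown. One limb of the causality rule in section 7.2 allows a Rituxan attribution when an event fits the drug's known pattern, and knowing the allocation could raise attribution as easily as lower it.
- A fatal excess would enter overall and progression-free survival, which section 1.2 compares between arms.
- A reader might want to say how far the 40-point benefit shrinks. No document gives an excess of severe events from adding rituximab. The infection percentages in section 7.1 compare two rituximab formulations, not rituximab with none.

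All of this stands and limits the point. None of it supplies the missing comparison of non-fatal, non-immune severe events. A descriptive Arm B rate is a coherent choice, but it cannot show whether such events are more frequent with Rituxan.

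**Conclusion.** The point holds as a gap in the specified analysis. The sole Rituxan safety endpoint rests on unblinded attribution and cannot occur in Arm A, and no randomised comparison of all-cause severe events, infections or SAEs is planned. A severe, non-fatal, non-immune excess in Arm B could fall outside both toxicity endpoints. The size of such an excess cannot be taken from the documents. The figures in steps 3 to 5 rest on assumed rates, and step 4 also on independence, so they show sensitivity and precision only.

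The primary comparison and its stated power are unaffected. The change is worth making because this trial is about toxicity and most of the necessary data are already called for. Complete all-cause data to 6 months in both arms are not assured until the passages in step 6 are reconciled.

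**What to change.** In sections 1.2 and 14.1, place ahead of the Rituxan-related rate the between-arm difference, with 95% confidence interval, in the proportion of patients with:

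- a grade 3 or greater infection;
- a grade 3 or greater non-immune adverse event;
- any grade 3 or greater adverse event regardless of attribution;
- any SAE;
- death not due to melanoma.

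Count each over the same 6 months from first ipilimumab/nivolumab as the primary endpoint, in all treated randomised patients. Present these as estimates, not powered tests. The non-immune line and the cause of death still need a judgement, so read them beside the any-cause line. Keep the Rituxan-related rate as a descriptive Arm B listing, and state which causality levels count as related: section 7.2 gives both a yes/no rule and a five-level scale.

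Reconcile the Schema and sections 5.2, 7.2 and 12.1.1 on who is in the safety set and how long adverse events are collected, so that both arms have complete attribution-free data over the window.

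The cost is endpoint wording, a few tables, an aligned collection window with possibly some added follow-up, and wide intervals: roughly 17 to 28 points either side with 22 per arm.

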14.2 Sample Size/Accrual Rate

This is an open-label, 2-arm phase II clinical trial to study the differential effect in the risk of IRAEs between treatment and control groups. A sample size of 22 patients per arm (44 total) will provide us approximately 80% power to detect a 40% difference in the rates of developing ≥grade 3 IRAE within 6 months follow up between the control and the treatment arm (estimated to be 60% in the control arm, Callahan et al; J Clin Oncol. 2017 Dec 1;35(34):3815-3822). The sample size calculation is based on Fisher's exact test at a one sided significance level of 0.05 under the following assumptions: 1). Patients will be randomized in 1:1 ratio of the treatment to control arm. 2). Approximately 60% patients in the placebo arm will develop > grade 3 IRAE

within 6 months based on our pilot study. 3). The treatment will reduce the rate of ≥ grade 3 IRAE to 20% in the treatment arm. In a recent study, the rate of objective response following combination checkpoint blockade was 42% (Callahan et al; J Clin Oncol. 2017 Dec 1;35(34):3815-3822). In order to monitor potentially adverse impact of Rituxan on checkpoint blockade, we will utilize early stopping rules based on an adaptive design wherein trial will be stopped if we have strong evidence of rates of objective response of <30%. The trial will be stopped early in the unlikely event that less than 2 patients among the first 12 patients treated by Rituxan respond to therapy. If the rate of objective response is > 30%, the probability that at least two out of first twelve patients will achieve an objective response of at least a PR for the first 12 patients is approximately 92%. Hazard ratios and corresponding two-sided 95% confidence intervals will be estimated using Cox-proportional hazards model, with the treatment group as a single covariate. Progression-free and overall survival curves, median with 95% confidence intervals, and progression-free survival rates at 6 months will be estimated with the use of Kaplan-Meier method. Biostatistics support for the study will be provided by biostatistics core resource of Winship Cancer Center.

Newly diagnosed patients as well as patients that have previously received anti-PD-1 therapy in adjuvant setting will be randomized as separate groups equally between the two arms. This will allow us to normalize the ORR between the two groups. ORR will be calculated for every 10 patients enrolled. The trial will be stopped early if there is a difference in ORR of greater than 30% between the two arms.

REFERENCES

- 4. Wolchok JD. PD-1 Blockers. Cell. 2015;162(5):937.

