5. TREATMENT PLAN

5.1 Agent Administration

Once the investigator has signed the eligibility checklist, randomization may proceed. Patients meeting study entry criteria will be randomized to treatment ARM A or Arm B by the study statistician, [name]. Eligible subjects (eligibility confirmed and checklist signed) will be assigned to a treatment arm until 44 subjects (22 in each arm) have been enrolled. The study coordinator will update Oncore and ERMS reflect randomization information.

Following randomization, patients should begin protocol treatment within 5 business days. Issues that would cause treatment delays should be discussed with the Principal Investigator.

Treatment will be administered on an *outpatient* basis. Reported adverse events and potential risks are described in Section 7. Appropriate dose modifications are described in Section 6. No investigational or commercial agents or therapies other than those described below may be administered with the intent to treat the patient's malignancy.

Patients will be randomly assigned 1:1 using block randomization with a block of 6 patients. Randomization schema will be kept in the research pharmacy.

Patients with unresectable stage III or stage IV melanoma being treated with FDA approved standard of care immune checkpoint combination therapy with Ipilimumab and Nivolumab are eligible for this trial.

Patients will be randomized 1:1 to either continue therapy with standard of care Ipilimumab and Nivolumab (ARM A) or standard of care Ipilimumab and Nivolumab plus **4 doses of weekly Rituxan** (ARM B).

Patients enrolling on this study following treatment failure on single agent anti-PD-1 will be distributed equally between arms A and B of the study.

Induction Phase:

ARM A: Cycles 1-4

Each cycle is 21 days and includes Ipilimumab (3 mg/kg) on day 1 plus Nivolumab (1 mg/kg) on Day 1.

ARM B. Cycles 1-4

Each cycle is 21 days and includes Ipilimumab (3 mg/kg) on day 1 plus Nivolumab (1 mg/kg) on

Version Date: 04-05-2021 v6.0

Day 1. In addition, patients will receive 4 weekly doses of Rituxan (first dose 375 mg/m2 IV and then 3 weekly doses of 1400 mg Rituxan Hycela subcutaneous, as per current label for Rituxan Hycela).

First dose of Rituxan will be administered 1 week after start of Ipi/Nivolumab therapy. 3rd dose of Rituxan will be administered on day 2 of cycle 2 after infusion of Ipi/Nivo on week4.

Continuation Phase:

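### Fisher's exact test uses about half of the 5% level that the plan allows and costs 3 to 9 points of power against Boschloo's test; the prior anti-PD-1 randomisation groups are defined in two ways and enter no stated analysis

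*Combined protocol and SAP*

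**What the plan says.** **Primary test.** Section 14.2 describes an open-label two-arm trial with 22 patients per arm. It assumes a rate of grade 3 or higher immune-related adverse events (IRAEs) within 6 months of 60% on control and 20% on Rituxan, and states about 80% power. The calculation rests on Fisher's "exact test at a one sided significance level of 0.05 under the following assumptions". No separate paragraph commits to a primary analysis, so this sentence is the only indication of the test.

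**Allocation.** Section 5.1 says "Patients will be randomly assigned 1:1 using block randomization with a block of 6 patients", and that subjects "will be assigned to a treatment arm until 44 subjects (22 in each arm) have been enrolled". It adds: "Patients enrolling on this study following treatment failure on single agent anti-PD-1 will be distributed equally between arms A and B of the study".

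**Groups.** The end of section 14.2 says that newly diagnosed patients and "patients that have previously received anti-PD-1 therapy in adjuvant setting will be randomized as separate groups equally between the two arms". The reason given is "This will allow us to normalize the ORR between the two groups".

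**Other analyses.** Hazard ratios come from a "Cox-proportional hazards model, with the treatment group as a single covariate". The objective response rate (ORR) check after every 10 patients is a plain difference between arms.

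**The concern.** Fisher's test conditions on the total number of events. In samples this small its attainable significance levels are coarse, so its true size can fall well below the nominal level. If the plan is willing to accept a 5% one-sided error but the test spends about half of that, power is given away that 44 patients could have delivered. This matters because the assumed 40-point reduction is large and power drops quickly for smaller effects.

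The two descriptions of the anti-PD-1 groups raise a practical problem. Staff must know which list each patient belongs to before allocation. The grouping is also justified by ORR, yet neither the ORR comparison nor any other analysis takes it into account.

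**Working it through.** **Inputs.** From section 14.2: 22 per arm, 60% against 20%, one-sided 0.05. From section 5.1: 1:1 allocation in blocks of 6.

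**Method.** For every pair (x control events, y Rituxan events), compute the one-sided Fisher p-value from the hypergeometric distribution.
- Power = sum of Bin(x; n1, 0.60) × Bin(y; n2, 0.20) over the rejected pairs.
- Size = the same sum with one common rate in both arms, maximised over rates from 0.0005 to 0.9995.
- Boschloo's test orders the tables by Fisher p-value and takes the largest rejection region whose maximum size is at most 0.05.

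**The plan's own figure.** Fisher at 22/22 gives power 0.7911 and maximum size 0.0249. The stated power of about 80% is reproduced.

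**Boschloo at 22/22.** The region is Fisher p ≤ 0.0926, with maximum size 0.0493. Adding the next table would raise the size to 0.0554. Power is 0.8696, a gain of 7.8 points.

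| Control/Rituxan | Fisher power | Boschloo power | Gain (points) |
|---|---|---|---|
| 22/22 | 79.1% | 87.0% | 7.8 |
| 21/23 | 80.4% | 86.1% | 5.7 |
| 23/21 | 79.4% | 85.6% | 6.3 |
| 20/24 | 82.2% | 85.5% | 3.3 |
| 24/20 | 80.6% | 85.7% | 5.1 |
| 21/22 | 82.3% | 85.6% | 3.3 |
| 22/21 | 80.6% | 86.5% | 5.9 |
| 21/21 | 76.1% | 84.7% | 8.7 |
| 22/23 | 82.8% | 86.0% | 3.2 |

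Over all 22 splits with 20 to 24 per arm and at most 46 patients, the gain is 3.2 to 8.7 points (mean 6.1). Fisher's maximum size is 2.4% to 3.3% and Boschloo's is 4.3% to 4.98%. At every split run, Boschloo rejects every table that Fisher rejects.

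**Which split is likely.** 44 = 7 × 6 + 2, so a single list stops two patients into a block. Those two fall 1-1 with probability 9/15 and 2-0 or 0-2 with 3/15 each. The mean gain is 0.6 × 7.845 + 0.2 × (5.7 + 6.3) = 7.1 points. With two lists of 22 (an assumption) it is 0.44 × 7.845 + 0.24 × (5.7 + 6.3) + 0.04 × (3.3 + 5.1) = 6.7 points.

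**Smaller effects at 22/22.** For 60% against 25%, power is 66.2% with Fisher and 76.8% with Boschloo. For 60% against 30%, it is 52.1% and 64.2%.

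**Price at 22/22.** If both arms share a rate of 20%, the false-positive rate rises from 2.4% to 4.9%; at 40%, from 2.3% to 4.6%.

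**What changes in practice.** With 13/22 control events, Fisher needs 6/22 or fewer on Rituxan. Boschloo also rejects at 7/22, where the Fisher p-value is 0.065.

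**The groups side by side.** Section 3.1 admits patients who progressed on single-agent anti-PD-1 without limiting this to adjuvant use.

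| Patient | Section 5.1 | Section 14.2 |
|---|---|---|
| Progressed on anti-PD-1 for metastatic disease | balanced | in neither group |
| Prior adjuvant anti-PD-1 | unclear whether this counts as failure | own group |
| Newly diagnosed | not mentioned | own group |

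The block-of-6 sentence in section 5.1 mentions no groups, so it is unclear whether separate lists exist.

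**What analysing by group would change (assumed inputs).** The documents do not say whether the groups differ in outcome.
- *ORR.* Take 42% overall (section 14.2), 22 per arm and the same group rates in both arms. The crude standard error of the difference is √(2 × 0.42 × 0.58 / 22) = 0.1488. With 11 patients per group per arm and a 20-point gap (52% and 32%), the stratified value is √(2 × 0.2336 / 22) = 0.1457. With a 40-point gap it is 0.1360. With groups of 18 and 4 per arm the values are 0.1470 and 0.1414. The reduction is therefore 1% to 2%, or 5% to 9%.
- *Cox.* 3,000 simulations with true hazard ratio 0.50, 11 patients per arm per group, control median 10 months in the lower-risk group and 24 months' follow-up, all assumed. With a group hazard ratio of 2, the unstratified model gives 0.519 and the stratified model 0.493. With a group hazard ratio of 3, they give 0.552 and 0.488.

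**The case against.** Fisher's test is valid, the trial meets its stated power with it, and a team may prefer an actual error rate near 2.5% to one near 5%. That stands, and it is why the test change is an improvement rather than a correction. A team that keeps Fisher should say so in a sentence naming the primary analysis.

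Timing is a stronger objection. This is version 6.0 of an open-label trial, and moving to a less conservative test partway through can look data-driven. The 13/22 against 7/22 example is exactly such a case. The documents do not show how far accrual has gone, so a statement that IRAE rates have not been compared by arm may no longer be possible. That limits the remedy, not the arithmetic.

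Section 5.1 also plans exactly 22 per arm, and the split probabilities assume how the lists end. The gain is nevertheless positive at every split examined, and largest among the 44-patient splits shown at 22/22 itself.

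On the groups, balanced allocation does some of the intended work without a stratified analysis, and the precision gained for ORR is small unless the groups differ a great deal. Part of the Cox shift arises because stratified and unstratified hazard ratios are different quantities. A treatment-only model is a legitimate choice in 44 patients. None of this resolves the conflict between the two definitions.

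**Conclusion.** The concern holds on both parts. At the planned 22 per arm, Boschloo's test raises power from 79.1% to 87.0% at the same nominal level with no extra patients. At nearby splits the gain is 3.2 to 8.7 points. These figures rest on the plan's 60% and 20% rates, assume no dropout, and ignore the ORR stopping rules. The plan's power statement is right and Fisher's test is valid, so the loss is one of efficiency.

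The mismatch between sections 5.1 and 14.2 is a plain textual conflict and needs no assumption. At least one kind of eligible patient has no group under section 14.2, and the grouping enters no stated analysis. How much a stratified analysis would gain cannot be settled from the documents; the illustrations suggest little for ORR unless the group gap is large.

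**What to change.** 1. In section 14.2, name the one-sided Boschloo exact test at 0.05 as the primary analysis and keep the Fisher-based sample size statement. Report the risk difference with a 90% interval, and the Fisher p-value as a sensitivity result so that readers can see whether the conclusion depends on the change. Date and document the change before any comparison of IRAE rates by arm, with a statement that none has been made.
2. Reconcile sections 5.1 and 14.2 into one prior anti-PD-1 factor that covers every patient eligible under section 3.1, for example any prior anti-PD-1, yes or no. State that block lists are kept per group, and classify patients already randomised from their recorded history.
3. Stratify the ORR comparison and the Cox model by that factor. The primary test does not need stratifying.

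**Cost.** The test needs no new data, but its actual false-positive rate about doubles at 22/22, within the nominal 5%. Boschloo's p-value and a separately computed interval can disagree near the boundary. The single factor changes the lists held in the research pharmacy and requires a check of anti-PD-1 history. The stratified Cox model has a slightly larger standard error (0.36 against 0.34 to 0.35 in the assumed cases).
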